#### **7.2.4 Sponsor Responsibility for Reporting Adverse Events**

All Adverse Events will be reported to regulatory authorities, IRB/IECs and investigators in accordance with all applicable global laws and regulations.

### **8.0 STATISTICAL ANALYSIS PLAN**

#### **8.1 Statistical Analysis Plan Summary**

This is an investigator initiated, open label, phase II clinical trial to evaluate the efficacy of the combination therapy of Pembrolizumab and fractionated external beam radiotherapy (EBRT) in patients with relapsed and refractory aggressive Non-Hodgkin lymphoma (NHL). The maximum number of patients that will be recruited for the study is 40.

The primary objective of the trial is to determine the overall response rate of Pembrolizumab and fractionated EBRT in patients with relapsed and refractory NHL. The secondary objectives are to evaluate the safety, CRR, PFS, OS and duration of response of pembrolizumab with concurrent fractionated EBRT. Patients will receive 200 mg IV of Pembrolizumab with concurrent EBRT at standard of care doses of 40-50 Gy of EBRT in fractions of  $\leq 3$  Gy.. The trial enrollment will be stratified according to the extent of relapsed/refractory disease included in the RT field(s) with 2 cohorts of patients enrolled based on the treated RT field. For Cohort 1, patients with aggressive NHL, will receive RT to 1-2 region(s) of disease and the ORR will be determined for a designated “unirradiated” lesion (Cohort 1). For patients with relapsed/refractory aggressive NHL in Cohort 2, RT will be administered to encompass all sites of radiographically evident disease in 1-2 RT plan(s), the ORR will be based on the disease treated within the RT field. **The maximum number of patients in each cohort is 20 with a total anticipated trial enrollment of 40 patients..**

Overall response rates to PD-1 blockade monotherapy among patients with hematologic malignancies is based on published data. For cohort 1, we assume that concurrent external beam radiation therapy with concurrent pembrolizumab will improve ORR (of the non-irradiated lesion[s]) over the reported rates of PD-1 blockade which are roughly 26% for B cell lymphoma and 17% for T cell lymphoma.

**While the ORR for definitive RT for patients with de novo aggressive NHL approach 100%, overall response rate to salvage RT for patients with refractory aggressive NHL treated with curative intent has been reported to be 78%, with a 5 year progression free survival rate of 34%. We assume that concurrent EBRT and pembrolizumab will improve the ORR when all sites of known disease are radiated.**

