It is likely that the timing of immune checkpoint blockade and EBRT influence the effectiveness of therapy. In a pre-clinical model of melanoma, breast and colorectal cancer, the anti-tumor activity of low dose fractionated RT was enhanced through the combination of a monoclonal antibody targeting PD-L1. In this mouse model, treatment timing and scheduling was significantly affected treatment efficacy; with concurrent RT and PD-L1 therapy but not sequential therapy resulting in beneficial local control and survival. Based on these data we propose that pembrolizumab and fractionated RT should be administered concurrently.

The overall response rates of refractory NHL to single modality radiation therapy are relatively high but often not durable. In a retrospective study from the Dana-Farber Cancer Institute of 110 patients treated with a course of salvage radiation therapy for relapsed or refractory aggressive NHL, the overall response rate was 78% among refractory patients treated with curative intent and 81% for those refractory patients treated with palliative intent. Among living patients the 5 year rate of progression free survival however was only 34%. Furthermore even among patients treated with doses greater than 40 Gy with curative intent the 2 year local control rate was only 61%. This highlights 1) the need for effective systemic therapies to pair with salvage radiation therapy and 2) the room for improvement in long term local control that for patients with refractory NHL that may be accomplished with concurrent systemic therapy.

Given this data this study will address the role of pembrolizumab and concurrent RT in two patient populations. The first eligible cohort will include patients with more disseminated disease where all disease will not be included in the radiation field and there will be an “unirradiated lesion”. The second cohort of eligible patients will be those with relapsed/refractory aggressive NHL where all sites of disease can be encompassed in 1-2 radiation therapy fields. We hypothesize that 1) the response rates of the unirradiated lesion will be higher than reported ORR among patients treated previously with PD-1 blockade monotherapy for relapsed and refractory NHL and 2) the response rates for patients treated

with pembrolizumab and RT fields encompassing all sites of disease will be also be improved over rates reported for salvage RT alone.

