### **7.1.2.6 Tumor Imaging and Assessment of Disease**

Tumor response will be assessed radiographically according to the revised Lugano classification for response assessment of HL and NHL. In patients with FDG avid disease contrasted PET-CT will be utilized for baseline imaging as well as for determination of tumor response according to the standard of care. For patients with non-FDG avid or FDG-variable disease, CT imaging will be utilized for baseline radiographic examination as well as for assessment of tumor response.

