- 1) Stop if  $\text{Prob}\{\theta_{\text{OR}} < 0.35 \mid \text{data}\} > 0.95$ , and
- 2) Stop if  $\text{Prob}\{\theta_{\text{DLT}} > 0.30 \mid \text{data}\} > 0.95$

Patients will be monitored by a cohort size of 10 according to the following stopping boundaries for OR at 3 months and DLT at cycle one. If the number of responses required for moving the trial to next stage has not been achieved, the patient enrollment will be halted until enough responses observed.

Number of patients evaluated	Stop if <= OR observed	Stop if >= DLT observed
10	0-1	6-10
20	Always stop with this many patients	

The operating characteristics are summarized in the following table (based on simulations from 10,000 trials).

True DLT Rate	True OR Rate	Prob (stop the trial early)	Average number of patients treated
0.1	0.15	0.5444	14.56
	0.25	0.2441	17.56
	0.35	0.0861	19.14
	0.45	0.0234	19.77
	0.55	0.0046	19.95
0.2	0.15	0.5472	14.53
	0.25	0.2488	17.51
	0.35	0.0918	19.08
	0.45	0.0295	19.71
	0.55	0.0108	19.89
0.3	0.15	0.5659	14.34
	0.25	0.2798	17.20
	0.35	0.1292	18.71

	0.45	0.0695	19.31
	0.55	0.0516	19.48
0.4	0.15	0.6201	13.80
	0.25	0.3697	16.30
	0.35	0.2379	17.62
	0.45	0.1856	18.14
	0.55	0.1700	18.30
0.5	0.15	0.7161	12.84
	0.25	0.5290	14.71
	0.35	0.4305	15.69
	0.45	0.3914	16.09
	0.55	0.3798	16.20

In cohort 2 patients will be treated to all sites of relapsed or refractory NHL that can be completely included in 1-2 RT field(s), we will consider that the regimen is promising if the OR rate of the radiated disease at 3 months is at least 90% and the DLT rate at cycle one is below 30%. A sample size of 20 ensures that, if the trial is not terminated early, a posterior 90% credibility interval for OR rate at 3 months will have width of 0.203 at most, when 18 responses are observed out of the 20 patients, under the assumption of 90% OR rate. The prior probability of OR and DLT for the regimen are modeled by beta distribution (*Beta*(0.9,0.1) and *Beta*(0.3,0.7), respectively). Denoting the probability of OR and DLT by  $\{\theta_{OR}, \theta_{DLT}\}$ , and they are compared to fixed targets of OR and DLT rates. The following decision criteria will be applied:

- 1) Stop if  $\text{Prob}\{\theta_{OR} < 0.90 \mid \text{data}\} > 0.95$ , and
- 2) Stop if  $\text{Prob}\{\theta_{DLT} > 0.30 \mid \text{data}\} > 0.95$

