**Table 3. Revised Criteria for Response Assessment (continued)**

Response and Site	PET-CT-Based Response	CT-Based Response
New lesions	New FDG-avid foci consistent with lymphoma rather than another etiology (eg, infection, inflammation). If uncertain regarding etiology of new lesions, biopsy or interval scan may be considered	Regrowth of previously resolved lesions A new node > 1.5 cm in any axis A new extranodal site > 1.0 cm in any axis; if < 1.0 cm in any axis, its presence must be unequivocal and must be attributable to lymphoma Assessable disease of any size unequivocally attributable to lymphoma
Bone marrow	New or recurrent FDG-avid foci	New or recurrent involvement

Abbreviations: 5PS, 5-point scale; CT, computed tomography; FDG, fluorodeoxyglucose; IHC, immunohistochemistry; LDi, longest transverse diameter of a lesion; MRI, magnetic resonance imaging; PET, positron emission tomography; PPD, cross product of the LDi and perpendicular diameter; SDi, shortest axis perpendicular to the LDi; SPD, sum of the product of the perpendicular diameters for multiple lesions.

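### Cohort 2 response is defined on irradiated disease only, with no rule for new lymphoma outside the field, which conflicts with the Lugano criteria the protocol adopts

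*Combined protocol and SAP*

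**What the plan says.** Two places define the Cohort 2 decision endpoint, and both limit it to irradiated disease. Section 8.1 states that "the ORR will be based on the disease treated within the RT field". Section 8.2 adds: "we will consider that the regimen is promising if the OR rate of the radiated disease at 3 months is at least 90" percent, together with a condition on the toxicity rate. The Beta(0.9, 0.1) prior, the 0-to-6-in-10 stopping boundary and the table of operating characteristics for Cohort 2 all follow from that definition. On size, section 8.1 says: "The maximum number of patients in each cohort is 20 with a total anticipated trial enrollment of 40 patients".

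Elsewhere the protocol commits to a whole-patient classification. Section 7.1.2.6 reads: "Tumor response will be assessed radiographically according to the revised Lugano classification". Sections 2.1, 4.2.2 and 11.3 say the same. In the criteria table in section 11.3, complete and partial response both carry the entry None for new lesions. The progressive disease rows include "New FDG-avid foci consistent with lymphoma rather than another etiology" on PET-CT, and new nodes or extranodal sites on CT.

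Section 4.2.2 states the Cohort 2 response rate without an in-field limit. It plans a split into local (in-field) and systemic (out-of-field) response on top of the overall rates. Section 3.1 also states the roughly 90% hypothesis without an in-field limit. The opening sentence of section 8.2 describes the monitored response as that of non-irradiated lesions, which Cohort 2 patients do not have at baseline.

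**The concern.** The same patient can be classified in two ways. Take a Cohort 2 patient whose irradiated disease has resolved at 3 months but who has new lymphoma in an unirradiated region. Under the adopted criteria that is progressive disease. Under sections 8.1 and 8.2, read plainly, it is a response, because only the irradiated disease is counted.

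This matters because the Cohort 2 count drives both the interim stop and the conclusion that the regimen is promising, and it is presented as the overall response rate of the primary objective. Out-of-field progression is an expected event: section 2.1 (Phase II Trial) provides for patients who progress outside the radiation field. Part of the rationale in section 4.2.1 is systemic: "This highlights 1) the need for effective systemic therapies to pair with salvage radiation therapy". A count confined to the field cannot register failure outside it.

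**Working it through.** **1. The plan's own figures reproduce.** Inputs from section 8.2: prior Beta(0.9, 0.1), n = 20, one interim look at 10, and a stop for response if the posterior probability that the rate is below 0.90 exceeds 0.95.

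- Precision at 18/20: the posterior is Beta(0.9 + 18, 0.1 + 2) = Beta(18.9, 2.1). The equal-tailed 90% interval is 0.777 to 0.980, width 0.203, as stated.
- Boundary at n = 10: the posterior is Beta(0.9 + r, 0.1 + 10 − r). The probability that the rate is below 0.90 is 0.989 at r = 6 (stop) and 0.940 at r = 7 (continue). This gives the stated 0 to 6.
- Early stopping: 1 − [1 − P(X ≤ 6)] × [1 − P(DLT ≥ 6)], by exact binomial. All 25 Cohort 2 rows match; for example, 0.0129 at response rate 0.9 and DLT rate 0.1.

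The arithmetic is sound. The issue is what counts as a response.

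**2. One patient can change a decision.** At the interim, 7/10 in-field responders means continue. If one of the seven has new lymphoma elsewhere, the Lugano count is 6/10 and the rule says stop. At the end, 18/20 = 90% meets the target; one such patient among the 18 gives 17/20 = 85%, which does not.

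**3. Illustrative size.** Assumptions, none of them in the documents: the true in-field response rate is 90%, and a share f of in-field responders has new out-of-field lymphoma by 3 months. Patient-level response is then p = 0.90 × (1 − f). The final criterion is taken as at least 18/20, the count that equals the 90% target and that section 8.2 uses for its precision statement. The toxicity rule is ignored.

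- P(at least 18/20) = 190p^18(1−p)^2 + 20p^19(1−p) + p^20. At p = 0.90 this is 0.285 + 0.270 + 0.122 = 0.677.
- Reaching 18/20 allows at most two failures, so the interim response rule (which needs at least four failures in 10) is passed automatically. The same figure is therefore the chance of passing both.
- P(interim response stop) = P(X ≤ 6) for n = 10.

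| f | patient-level p | P(interim stop) | P(≥18/20) |
|---|---|---|---|
| 0 (in-field scoring) | 0.900 | 1.3% | 0.68 |
| 5% | 0.855 | 4.5% | 0.43 |
| 10% | 0.810 | 10.4% | 0.24 |
| 20% | 0.720 | 29.8% | 0.05 |

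Under in-field scoring the first row applies whatever f is.

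**The case against.** **No sentence says that such a patient is a responder.** This is correct. Section 8.2 defines response as complete plus partial response, and Lugano is the only definition of those terms in the documents. Since all baseline disease in Cohort 2 lies in the field, section 8.1 could be read as merely naming the target disease, with Lugano still classifying the patient. That reading is possible. However, sections 8.1 and 8.2 both speak of the irradiated disease, section 4.2.2 has a separate category for in-field response, and no text applies the new-lesion rule to this count. The text needs reconciling on either reading.

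**In-field scoring may be deliberate.** Both cohorts use field-based endpoints, and the sentence in section 4.2.1 that calls for systemic therapy goes on to cite room for better long-term local control. A reader might infer that Cohort 2 exists only to show a systemic effect; the documents do not support that. Still, a 3-month in-field rate does not measure long-term local control, and it is labelled an overall response rate.

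**The 78% benchmark.** A reader might infer that once enough responders have out-of-field disease (about 13%, since 0.90 × 0.87 = 0.783), the regimen does no better than radiotherapy alone. The documents do not say whether the 78% was scored in the field or on the whole patient. Calling it an overall response rate settles nothing, because section 8.1 uses the same term for a single unirradiated lesion. No comparison with it is made here.

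**Out-of-field failure is captured elsewhere.** It is, through systemic response, progression-free survival and duration of response. None of these enters the 90% target or the stopping boundary.

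**Not every new lesion is progression.** This also stands. Lugano requires a lesion consistent with lymphoma and allows biopsy or an interval scan, and sections 4.2.2 and 7.1.2.6.4 provide for confirmation.

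**Conclusion.** The Cohort 2 decision endpoint is not reconciled with the response criteria the protocol adopts. On the plain reading, in-field response with new lymphoma elsewhere at 3 months is a success, so the reported figure is biased upward as an overall response rate. The direction follows from the definition, because in-field responders include everyone who would respond at patient level. The size is unknown. The values in the table depend on an assumed 90% in-field rate and an assumed 5% to 20% out-of-field share, and they set the toxicity rule aside. They show that a modest share is enough to change the conclusion in a cohort of 20. They do not show that it will change.

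**What to change.** - In sections 8.1 and 8.2, define Cohort 2 response at 3 months as patient-level Lugano complete or partial response. A new lesion outside the field that meets the Lugano definition is then a non-response, after any biopsy, interval scan or confirmation that the protocol already allows.
- Report in-field response beside it, labelled local response as section 4.2.2 plans.
- Correct the opening sentence of section 8.2 so that it does not describe Cohort 2 response in terms of non-irradiated lesions.

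If the sponsor keeps the in-field endpoint, it should be called a local response rate, with the 3-month patient-level Lugano rate reported beside it. The conclusion that the regimen is promising should then not rest on local response alone.

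The same scans serve, so no new data are needed. The cost is more than wording, however. The 90% target, the Beta(0.9, 0.1) prior and the 0-to-6 boundary were set for irradiated disease, and the sponsor must confirm that they still suit the patient-level rate or justify new ones. If they are kept, the interim stop becomes more likely, as the table shows, and the reported rate may be less favourable.

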## 1.0 TRIAL SUMMARY

Abbreviated Title	Pembrolizumab (MK-3475) and radiation for relapsed and refractory Non-Hodgkin Lymphoma
Trial Phase	II
Clinical Indication	Refractory Non-Hodgkin Lymphoma
Trial Type	Treatment (Interventional)
Type of control	Historical Control
Route of administration	Intravenous and external beam radiation
Trial Blinding	Unblinded, open label
Treatment Groups	MK-3475 200 mg every 21 days with concurrent External beam radiation therapy (EBRT)
Number of trial subjects	21
Estimated enrollment period	20 months
Estimated duration of trial	48 months
Duration of Participation	1.5 years
Estimated average length of treatment per patient	24 months

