### 3.0 OBJECTIVES & HYPOTHESES

#### 3.1 Primary Objective & Hypothesis

- 1) **Primary Objective:** To determine the overall response rate (ORR) of pembrolizumab with concurrent fractionated EBRT among patients with relapsed and refractory NHL.

**Hypothesis:** Therapy with pembrolizumab concurrent with EBRT will result in an ORR of at least 35% in unirradiated lesions among patients with relapsed and refractory NHL and roughly 90% among patients with relapsed and refractory NHL treated comprehensively to all sites of radiographically apparent disease that can be encompassed in 1-2 radiation therapy fields.

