#### **8.2 Statistical Analysis Plan**

Phase II design:

The overall response (OR: complete response + partial response) of non-irradiated lesion(s) at three months and dose limiting toxicity (DLT) at one cycles (3 weeks) will be monitored simultaneously using the Bayesian stopping boundaries calculated based on beta-binomial distributions. Independence is assumed between OR and DLT.

DLT is defined as the following toxicities observed during cycle one of the treatment that are considered by the investigator to be related to therapy:

1. Grade 4 neutropenia (ANC < 500/mm3) lasting more than 7 consecutive days.
2. Grade 3 neutropenia with fever and/or infection, where fever is defined as an oral Temperature  $\geq 38.5^{\circ}\text{C}$ .
3. Grade 4 thrombocytopenia (platelets < 25,000/mm3) lasting more than 7 consecutive Days.
4. Grade 3 thrombocytopenia with clinically significant bleeding.
5. A platelet count < 10,000/mm3 at any time.
6. Grade 3 or greater nausea and/or emesis despite the use of optimal anti-emetic Prophylaxis. Optimal anti-emetic prophylaxis is defined as an anti-emetic regimen that employs a 5-HT3 antagonist given in standard doses and according to standard schedules.
7. Grade 3 or greater diarrhea that occurs despite maximal supportive therapy.
8. Any other Grade 3 or greater non-hematologic toxicity with the following exceptions: Grade 3 arthralgia/myalgia or brief (< 1 week) Grade 3 fatigue.
9. A delay of more than 2 weeks in the initiation of Cycle 2 of treatment because of a lack of adequate recovery of therapy related hematological or non-hematologic toxicities.

In cohort 1 for the patients with multiple sites of aggressive NHL, we will consider that the regimen is promising if the OR rate of the non-irradiated lesion (s) at 3 months is at least 35% and the DLT rate at cycle one is below 30%. A sample size of 20 ensures that, if the trial is not terminated early, a posterior 90% credibility interval for OR rate at 3 months will have width of 0.335 at most, when 7 responses are observed out of the 20 patients, under the assumption of 35% OR rate. The prior probability of OR and DLT for the regimen are modeled by beta distribution ( $\text{Beta}(0.35, 0.65)$  and  $\text{Beta}(0.3, 0.7)$ , respectively). Denoting the probability of OR and DLT by  $\{\theta_{\text{OR}}, \theta_{\text{DLT}}\}$ , and they are compared to fixed targets of OR and DLT rates. The following decision criteria will be applied:

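### Does Cohort 1 need a formal comparison with PD-1 monotherapy response rates, beyond its 35% target?

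*Combined protocol and SAP*

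**What the plan says.** The plan makes two kinds of statement about Cohort 1.

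- **A numerical hypothesis.** Section 3.1 states that treatment "will result in an ORR of at least 35% in unirradiated lesions among patients with relapsed and refractory NHL". Section 8.2 turns this into a two-part criterion for calling the regimen promising, covering response outside the radiation field and toxicity: "lesion (s) at 3 months is at least 35% and the DLT rate at cycle one is below 30" percent.
- **An expectation relative to history.** Section 1.0 gives the type of control as "Historical Control". Section 4.2.1 hypothesises that "the response rates of the unirradiated lesion will be higher than reported ORR among patients treated previously with PD-1 blockade monotherapy". Section 8.1 puts numbers to this, assuming an improvement "over the reported rates of PD-1 blockade which are roughly 26% for B cell lymphoma and 17% for T cell lymphoma".

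The analysis in section 8.2 uses beta posteriors for OR and DLT, and "they are compared to fixed targets of OR and DLT rates" (0.35 and 0.30). There is one look at 10 patients, stopping for 0–1 responses or 6–10 DLTs. At 20 patients the boundary table says only "Always stop with this many patients". The operating-characteristics table has a column headed "Prob (stop the trial early)" and a column for average sample size. The Analysis Plans text gives each cohort's response rate with a 95% confidence interval and names no reference rate.

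**The concern.** A trial that declares a historical control and expects to beat it would normally say how the result will be set against that control. Here the historical rates appear in the motivation and then drop out. Nothing at 20 patients refers to 26% or 17%, and the table does not show how often an unimproved regimen would still be called promising.

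The stake is over-reading. A result of 7/20 meets the 35% criterion exactly and could be presented as evidence that radiation adds to PD-1 blockade, although so small a sample cannot separate 35% from 26%. The historical rates are also soft. The 26% is 8 of 31 patients given nivolumab, counted by patient and not by a designated unirradiated lesion, and it includes follicular lymphoma, an indolent histology that section 5.1.2 excludes. The DLBCL row of the same table is 4/11 (36%), already at the target.

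**Working it through.** **Inputs.** From section 8.2: Beta(0.35, 0.65) prior for OR and Beta(0.3, 0.7) for DLT, OR and DLT independent, one look at n = 10, maximum n = 20. From section 8.1: historical rates of 26% and 17%. From the Figure 3 table in section 4.2.1: B-cell 8/31, FL 4/10, DLBCL 4/11, T-cell 4/23.

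**Step 1: reproduce the plan's own figures.** The trial continues past n = 10 if there are at least 2 responses and at most 5 DLTs, so P(stop early) = 1 − P(X_OR ≥ 2 of 10) × P(X_DLT ≤ 5 of 10).

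- OR 0.25, DLT 0.1: 1 − 0.7560 × 0.9999 = 0.2441 (plan: 0.2441).
- OR 0.35, DLT 0.3: 1 − 0.9140 × 0.9527 = 0.1292 (plan: 0.1292).

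All 25 Cohort 1 entries agree to rounding. The 90% credible interval at 7/20, from Beta(7.35, 13.65), is 0.191 to 0.526, a width of 0.335 as stated.

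**Step 2: translate 'promising' into counts.** The plan gives none. As observed rates at n = 20, at least 35% is at least 7 responses and below 30% is at most 5 DLTs. Posterior means give the same cut-offs: 7.35/21 = 0.35 for 7 responses, and 6.3/21 = 0.30 for 6 DLTs, which is not below 0.30.

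**Step 3: chance of 'promising'.** This is P(at least 2 responses in the first 10 and at least 7 in 20) × P(at most 5 DLTs in the first 10 and at most 5 in 20). The DLT factor is 0.989, 0.804 and 0.416 at true DLT rates of 10%, 20% and 30%.

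| True OR rate | Response part | DLT 10% | DLT 20% | DLT 30% |
|---|---|---|---|---|
| 17% (T-cell) | 0.040 | 4.0% | 3.2% | 1.7% |
| 19% (B-cell without FL) | 0.067 | 6.7% | 5.4% | 2.8% |
| 26% (B-cell as quoted) | 0.242 | 24.0% | 19.5% | 10.1% |
| 35% (target) | 0.576 | 57.0% | 46.3% | 24.0% |

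The 19% row removes the excluded histology: (8 − 4)/(31 − 10) = 4/21.

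**Step 4: sensitivity to the reading.** If 8 responses were needed, the response part at 26% would fall from 24.2% to 12.2%, and at the 35% target from 57.6% to 39.7%. If 6 DLTs were allowed, the range at 26% would be 14.7% to 24.2%.

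**Step 5: what the planned interval already shows.** Exact 95% limits, and the posterior probability that the rate exceeds 26%:

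| Responses of 20 | Exact 95% CI | Pr(rate > 0.26) |
|---|---|---|
| 7 | 15.4% to 59.2% | 0.80 |
| 8 | 19.1% to 63.9% | 0.91 |
| 9 | 23.1% to 68.5% | 0.96 |
| 10 | 27.2% to 72.8% | 0.99 |

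At 7/20 the interval covers both historical rates. It excludes 17% from 8/20 and 26% from 10/20. Anyone who sets the planned interval beside the rates quoted in section 8.1 sees directly that 7/20 does not establish improvement.

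**The case for a change.** The best case for a change is that the improvement hypothesis is written down, carries numbers and is never analysed. Fixing the comparison before results are known would prevent a benchmark being picked afterwards, and the additions would be cheap: one posterior probability and one table column. At 7/20, Pr(rate > 0.26) is only 0.80, and it falls to 0.74 if the uncertainty in 8/31 is allowed for with a Jeffreys posterior (an assumption). If the cohort were mostly DLBCL and the true rate were 36%, the response part of 'promising' would be met 61% of the time with no radiation effect at all.

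Much of this is true. Meeting 35% does not by itself show improvement over monotherapy, and the table would tell the reader more with a column for the chance of 'promising'. But the plan does not claim otherwise. Its primary objective is to determine the response rate, its numerical hypothesis is 35%, and section 8.2 addresses that value. Improvement over history is stated as an assumption in section 8.1 and as a hypothesis in the rationale, and it is reflected in a target set above both quoted rates.

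The benchmark argument also cuts both ways. DLBCL alone raises the comparator to 36%, on 11 patients (exact 95% CI 11% to 69%). Dropping the ineligible FL lowers it to 19%. A comparator weighted to the enrolled histologies cannot be fixed in advance, and several eligible histologies, such as primary mediastinal and transformed lymphomas, have no row of their own in the table. Formalising any one of these would lend precision to numbers that do not have it.

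**Conclusion.** The observation is accurate, but no change follows. Followed as written, the plan tests its own 35% hypothesis, stops early on rules whose operating characteristics reproduce, reports an interval that can be compared with any historical rate, and describes success only as promising. None of its stated numbers or rules is wrong. Added probabilities or caveats would be descriptive and would leave the target, stopping boundaries, sample size and permitted conclusions as they are.

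The chance of 'promising' with no improvement is 10% to 24% if the monotherapy rate is 26%, about 2.8% to 6.7% if it is 19%, and 1.7% to 4.0% if it is 17%, for true DLT rates from 30% down to 10%. At the 35% target the chance is 24% to 57%. These figures rest on reading 'promising' as at least 7/20 responses with at most 5/20 DLTs, and on the plan's assumption that OR and DLT are independent. A trial report should present a result near 35% with its interval and should not describe it as superiority over monotherapy. An analyst would do that from the plan as it stands.
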